9.2 Primary Endpoint(s)

9.2.1 Primary Variable Analysis

The primary efficacy endpoint is the ovulation rate calculated as the proportion of subjects who had at least one post-baseline P4 level ≥ 6 ng/mL or pregnancy confirmed by at least 2 positive serum β -hCG tests or detection of gestational sac on transvaginal ultrasound (TVUS). The denominator will be based on all subjects in the FAS. Subjects who do not have a confirmed pregnancy, or at least one P4 level ≥ 6 ng/mL due to the P4 levels never reaching this threshold, missing data, early withdrawal, or any other reason will be counted as not having ovulation (treatment failure).

The primary efficacy analysis will compare the pooled ovulation rate of LutrePulse OmniPod SC 20 μ g and 15 μ g to placebo. Let $P_{high+middle}$ and $P_{placebo}$ be the underlying ovulation rates in the combined middle- and high-dose arms and the placebo arm, respectively. The hypotheses for the one-sided statistical testing are:

$$H_0: P_{high+middle} \leq P_{placebo},$$

VS.

$$H_0: P_{high+middle} > P_{placebo}.$$

The hypotheses are tested using a stratified one-sided Fisher's exact test (Jung et al., 2014) in the FAS including the randomization scheme as the stratification factor. The SAS PROC FREQ with permutation-based Cochran-Mantel-Haenszel test with exact p-value derived from all possible permutations will be employed for the calculation of p-value for the stratified Fisher's exact test.

Date: 07 Dec 2017 E-Statistical Analysis Plan-21977; Ver.1.0 Supersedes: None Page 21 of 59

Jung has shown that the stratified Fisher's exact test is equivalent to the exact stratified Mantel-Haenszel test when exact p-value is derived from all possible permutations.

9.2.1.1 Bayesian Adaptive Design Rules

This section provides details for the decision rules to be implemented in the Bayesian adaptive study design.

Success criterion using group sequential strategy

To account for the multiplicities introduced by early success interim analyses, Pocock boundaries are used. Thus, the success threshold at each analysis corresponds to a nominal p-value < 0.0131 to maintain an overall one-sided type I error rate of 0.025.

The simulation results in Figure 13 for Scenario 7 in Section 15.2.3, as well as the justification provided in Section 15.2.4, show that the type I error is well controlled under the null hypothesis using the success boundary.

Futility criterion

Given the data collected at each interim time point, we compute the Bayesian predictive probability that the primary analysis will meet the success threshold once all arms have n = 15 subjects. If the predictive probability is less than 0.05, then the trial will be declared as a failure and terminate at this point due to futility.

The Bayesian predictive probability is calculated in the following fashion. First, for each arm d, we determine the number of future subjects required to complete the study, m_d . Then, the number of future responders occurring in arm d, Z_d , is generated from a Beta-Binomial distribution:

$$(Z_d | n_d, x_d) \sim BetaBinomial(m_d, a + x_d, b + n_d - x_d),$$

where n_{d} , x_{d} are the numbers of subjects and responders in arm d observed at interim analysis, and a non-informative prior Beta distribution with parameters a = 0.5 and b = 0.5 is used independently for each arm.

A large number of predicted values are sampled from the Beta-Binomial distribution for each arm, resulting in 1000 "complete" datasets. The predictive probability of eventual trial success is then the proportion of these complete datasets for which the primary analysis success threshold is met (p-value < 0.0131).

Dropping the low dose

If the observed response rate for the low dose meets the condition in inequality (2), then low dose will be dropped from additional enrolment, should the trial need to continue with the high dose, middle dose and placebo to assess the primary efficacy endpoint at the next analysis timing.

The remaining sample size that had been planned for the low dose will be reallocated among the remaining arms. Thus the sample size for the placebo, middle, and high doses may either be 9, 12, 15, 16, or 17 subjects, depending on whether early success is declared, and whether low dose is dropped at the first or second interim analysis.

The 20% threshold to drop low dose is chosen based on the ED80 dose-selection rule, as the maximum of the most effective treatment effect can reach 100% (with the success rate in the placebo group expected to be close to 0). It ensures that when the threshold is met, the low dose does not qualify as the ED80 dose. Furthermore, we present in Table 3 below the Bayesian predictive probabilities of selecting low dose as ED80, should it proceed to a later analysis, for a range of borderline interim analysis observations where the 20% threshold is just met. A non-informative prior Beta (0.5, 0.5) is used for all treatment arms and 10000 predictions were generated. The results show that such probabilities are small: <10% in all cases and <5% in all but three cases. Therefore, 20% is a justifiable choice for the threshold to drop low dose early.

Table 3 Bayesian Predicted Probability of Selecting Low Dose as ED80 at a Later Analysis when Low Dose was Dropped Early

		rxnary	ois when L	in Dust was	, Dropp	cu Larry
N per arm	N per arm	Observe	d n (%) of su	ccesses at	Diff*	Probability of
at interim	at later	interim analysis			(%)	selecting low dose as
analysis	analysis	High-dose	Mid-dose	Low-dose		ED80 if continue
						with low dose
9	12	6 (67.8)	4 (44.4)	3 (33.3)	-22.2	0.0207
		5 (55.6)	5 (55.6)	3 (33.3)	-22.2	0.0735
		5 (55.6)	4 (44.4)	2 (22.2)	-27.8	0.0059
		5 (55.6)	3 (33.3)	2 (22.2)	-22.2	0.0062
		4 (44.4)	4 (44.4)	2 (22.2)	-22.2	0.0159
	15	6 (67.8)	4 (44.4)	3 (33.3)	-22.2	0.0304
		5 (55.6)	5 (55.6)	3 (33.3)	-22.2	0.0672
		5 (55.6)	4 (44.4)	2 (22.2)	-27.8	0.0136
		5 (55.6)	3 (33.3)	2 (22.2)	-22.2	0.0201
		4 (44.4)	4 (44.4)	2 (22.2)	-22.2	0.0555
12	15	8 (75.0)	6 (50.0)	4 (33.3)	-25.0	0.0015
		7 (58.3)	6 (50.0)	4 (33.3)	-20.9	0.0231
		7 (58.3)	5 (41.7)	3 (25.0)	-25.0	0.0012
		7 (58.3)	4 (33.3)	3 (25.0)	-20.8	0.0014
		6 (50.0)	5 (41.7)	3 (25.0)	-20.8	0.0211
		6 (50.0)	4 (33.3)	2 (16.7)	-25.0	0.0011
		5 (41.7)	5 (41.7)	2 (16.7)	-25.0	0.0059
		5 (41.7)	4 (33.3)	2 (16.7)	-20.8	0.0173

Diff* is the difference in observed success rates between the low-dose group vs. the pooled high- and mid-dose groups

Dose-response evaluation and dose-selection

For trials that meet the primary analysis success threshold, we will subsequently select the ED80 dose, the lowest effective dose satisfying inequality (2). The ED80 dose will be labeled as such in the primary efficacy analysis table.

• As noted earlier, when the primary efficacy success is already declared at an interim analysis, but the success rate in the low-dose arm is not sufficiently low compared to the combined low- and high-dose success rate, the trial will continue to enroll more patients in the three dose arms only. Although no additional patients will be randomized to placebo, the success rate estimated from the enrolled placebo patients will be used in inequality (2) to determine the ED80 for the study.

Date: 07 Dec 2017 E-Statistical Analysis Plan-21977; Ver. 1.0 Supersedes: None Page 23 of 59

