In the third example (Figure 4), the pooled response rate at the first interim is 44.4% (8 total responders, with 3 on the middle dose and 5 on the high dose) versus 0% on placebo. The p-value is 0.0197 which does not meet the early success threshold. The predictive probability of eventual trial success is 86.1%, so the trial does not stop for futility. The low dose response rate is only 22.2%, which is more than 20% lower than the pooled response rate. Thus, the low dose is dropped, and accrual continues on the placebo, middle, and high dose arms.

The second interim occurs when the remaining arms each have 12 subjects. Since the last interim, there is one new responder on the high dose, and no new responders on the placebo or middle dose arms. The p-value for the pooled versus placebo is 0.0139, which is not sufficient to declare early success. The predictive probability is still above the futility threshold, so the trial continues to the final analysis.

Since the low dose was dropped at the first interim with only 9 subjects, the remaining 6 slots that would have been allocated to the low dose have been redistributed to the remaining arms. Thus, each arm at the final analysis has n = 17 subjects rather than n = 15. The p-value for the Fisher Exact test is 0.0011, so the trial meets success at the final analysis. The high dose is selected as the ED80.

[figure not shown]

Figure 4 Simulation results from Example Trial 3

At the first interim of example trial 4 (Figure 5), the response rate is a modest 20-30% on the investigational arms. No responses were observed on the placebo. The trial does not declare early success, but has high enough predictive probability to continue. Additionally, the low dose is not sufficiently lower than the pooled arms to be dropped. Thus, the trial continues enrolling subjects to all arms.

At the second interim, there are n=12 subjects allocated to each arm. No additional responses were observed on the low dose, which had only 2 responders (16.7%). The response rate for the pooled middle and high doses is now 41.7%. Neither the early success nor futility criteria were met. However, the low dose response rate is no longer within 20% of the pooled, so it will be dropped. The 3 remaining slots for the low dose are redistributed so that each remaining arm will receive one additional subject.

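### The SAP's futility rule projects to 15 per arm even when its own final analysis will have 16 or 17, so it can stop trials that its own model would continue

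*SAP*

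**What the plan says.** SAP 9.2.1.1 (Futility criterion) defines the Bayesian predictive probability as the chance that "the primary analysis will meet the success threshold once all arms have n = 15 subjects". The consequence is firm: "If the predictive probability is less than 0.05, then the trial will be declared as a failure". No exception is made for a dropped low dose. For the future data, "we determine the number of future subjects required to complete the study" in each arm (m_d), and "a non-informative prior Beta distribution with parameters a = 0.5 and b = 0.5 is used independently for each arm". The probability is estimated by simulation: "A large number of predicted values are sampled from the Beta-Binomial distribution for each arm", giving 1000 completed datasets. Success means that "the success threshold at each analysis corresponds to a nominal p-value < 0.0131".

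The next part of the same section (Dropping the low dose) reallocates the unused low-dose slots: "Thus the sample size for the placebo, middle, and high doses may either be 9, 12, 15, 16, or 17 subjects". Example Trial 3 in SAP 15.2.2 drops the low dose at the first look and says: "Thus, each arm at the final analysis has n = 17 subjects rather than n = 15". Example Trial 4 drops it at the second look and finishes with 16 per arm. The Scenario 4 text in SAP 15.2.3 uses the same sizes.

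**The concern.** Once the low dose has been dropped, a final analysis at 15 per arm is no longer in the plan. A probability computed for 15 leaves out future active subjects who will be enrolled: four of them after a first-look drop (17 instead of 15, in two active arms). The rule ends the trial, and SAP section 11 has the monitoring committee work from it. A stop that the design's own model would not support is hard to recover from in a population that the protocol (1.1) describes as very rare. The branch is common: SAP 15.2.3 reports that about half of Scenario 5 trials drop the low dose at the first look and continue with the other arms.

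**Working it through.** **Inputs.** From the SAP: Beta(0.5, 0.5) prior per arm, success at one-sided p < 0.0131, stop below 0.05, looks at 9 and 12 per arm, final size N = 15, 16 or 17. Assumption: unstratified Fisher's exact test, pooled middle and high doses against placebo. It returns the p-values of the SAP's example trials (0.0052, 0.0197, 0.0139).

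**Formula.** With n subjects and x_d responders in arm d, future responders are Z_d ~ BetaBinomial(N − n, 0.5 + x_d, 0.5 + n − x_d). The predictive probability is the total probability of all (Z_placebo, Z_middle, Z_high) for which the final Fisher p is below 0.0131. At these sizes it can be enumerated exactly.

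**Reproducing the SAP.**
- Example Trial 5 (0/9, 1/9, 2/9): exact 0.012, stated 0.015 (Monte Carlo standard error about 0.003).
- Example Trial 3 (0/9, 3/9, 5/9): exact 0.875 at N = 15, stated 0.861 (standard error 0.010).
- Power: 0.913, 0.811 and 0.433 in Scenarios 4, 5 and 6; stated 0.910, 0.807 and 0.428.

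**Which N did the SAP's simulations use?** Scenario 4 reports 122 of 10,000 trials stopped for futility at the second look after a first-look drop. Projecting to 15 gives 118 exactly, or 137 with 1000-draw noise. Projecting to the actual size gives 37. The sampling error of the count is about √122 ≈ 11, so 15 fits and 17 does not.

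**Why N matters.** With no placebo responders and y pooled responders, p = C(2N, y)/C(3N, y). For y = 9 this is 0.0161, 0.0167 and 0.0172 at N = 15, 16 and 17. For y = 10 it is 0.0094, 0.0099 and 0.0103. So 10 responders are needed at every N. From 6/24 at the second look, four more must come from 6 future active subjects at N = 15, but from 10 at N = 17.

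**Second look, low dose dropped at the first:**

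| Placebo | Pooled (middle/high) | N = 15 | N = 17 |
|---|---|---|---|
| 0/12 | 6/24 (0/6) | 0.018 | 0.236 |
| 0/12 | 6/24 (1/5) | 0.041 | 0.240 |
| 0/12 | 6/24 (2/4) | 0.053 | 0.243 |
| 0/12 | 6/24 (3/3) | 0.056 | 0.245 |
| 0/12 | 5/24 (range over splits) | 0.001–0.005 | 0.047–0.071 |
| 1/12 | 8/24 (more even splits) | about 0.02 | 0.06–0.07 |

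The 1/5 state is reachable. At the first look, placebo 0/9, low 0/9, middle 1/9, high 3/9 has probability 0.068, so the trial continues. The low dose is dropped because 0 < 4/18 − 0.2 = 0.022. Two more high-dose responders then lead to 1/12 and 5/12.

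**Whole design, exact probabilities, projecting to 15 versus the applicable size:**

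| Scenario (placebo, low, middle, high) | Second-look futility | All futility | Power |
|---|---|---|---|
| 4 (0.01, 0.10, 0.40, 0.50) | 2.0% → 1.2% | 4.6% → 3.4% | 0.913 → 0.917 |
| 5 (0.01, 0.10, 0.40, 0.40) | 4.2% → 2.6% | 9.8% → 7.9% | 0.811 → 0.818 |
| 6 (0.01, 0.10, 0.20, 0.40) | 13.6% → 9.6% | 36.4% → 30.8% | 0.433 → 0.445 |

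Before rounding, the power gains are 0.9172 − 0.9125 = 0.0047, 0.8178 − 0.8114 = 0.0064 and 0.4453 − 0.4329 = 0.0124.

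**Monte Carlo noise, a separate effect.** Near 0.05 the standard error with 1000 draws is √(0.05 × 0.95/1000) ≈ 0.007. A state whose exact value is 0.0527 (the 2/4 split) is stopped about 33% of the time. In Scenario 5, simulating the rule with 1000 draws gives 10.65% futility, against 10.6% stated and 9.8% exact.

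**The case against.** The case for leaving the rule alone has several parts.

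- **Disclosed performance.** The SAP's simulations fit the 15-per-arm rule, so its stated powers already carry the cost. A reader might infer that power is overstated or type I error inflated; neither follows. This stands.
- **Planning assumptions.** At 60–70% against 1%, Scenario 1 shows early futility of 0.000, and exact enumeration gives about 0.03%. The loss appears only at weaker effects. This stands.
- **The 24% figure.** A reader might infer that trials stopped by the mismatch typically have about a 24% chance of success. They do not. Exact stops in the 0/12, 6/24 state after a first-look drop are 0.13%, 0.25% and 1.7% of trials in Scenarios 4, 5 and 6. In Scenarios 4 and 5 the most frequent affected state is 1/12 with 8/24, which is barely above the cut at 17. The 2/4 and 3/3 splits of 6/24 pass the exact rule anyway, so their roughly fourfold gap does not describe wrongful stops.
- **Attribution.** A reader comparing the SAP's reported futility with an exact calculation at the applicable size might credit the whole gap to the projection size. Part of it is simulation noise.
- **Wording.** The m_d phrase could be read as the enlarged size, and Example Trial 3 reports the futility check before the drop, so 15 can be defended at the moment of the first look. But 15 is the only number given, the simulation counts match it, and at a second look after a first-look drop no such defence remains.
- **Discretion.** The protocol (9.6.1) and the opening of SAP section 9 phrase the futility stop permissively. The committee would still be given a probability for the wrong final size, and 9.2.1.1 is firm.

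**Conclusion.** The inconsistency is real and lies in a rule that ends the trial. After a low-dose drop the rule can stop a trial whose predictive probability, under the SAP's own model and final size, is above 0.05. Near the worst case that probability is about 0.24, nearly five times the cut-off. The average effect is modest: second-look stops that the applicable size would have avoided are 0.9%, 1.7% and 4.7% of trials in Scenarios 4, 5 and 6, for a power loss of about 0.5 to 1.2 points. The use of 1000 draws is a second, smaller weakness.

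These figures rest on unstratified Fisher tests, looks at exactly 9 and 12 per arm, the stated priors, and a low-dose decision taken before the futility check in the applicable-size calculation. This should be corrected before an interim analysis is run. It does not undermine the design's stated power or error control.

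**What to change.** In SAP 9.2.1.1, define m_d as the final per-arm size that applies given the low-dose decision (15 with no drop, 17 after a drop at the first look, 16 after a drop at the second) minus the current number in that arm. State that the low-dose decision is evaluated before the futility check at each look. Replace the 1000 draws with exact beta-binomial enumeration. Re-run the operating characteristics in SAP 15.2.3 and bring the separate interim-analysis document into line.

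The cost is a sentence or two, a small code change and a repeat of the simulations. The downside is that a few more trials run to the planned maximum: total futility stops fall by 9.8 − 7.9 = 1.9 points in Scenario 5 and 36.4 − 30.8 = 5.6 points in Scenario 6. If the sponsor prefers the stricter rule, the SAP should say that projecting to 15 is deliberate and why.

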The trial stopped for futility 4.7% of the time (240 trials at the first interim and 232 trials at the second interim). Since the low dose is much lower than the middle and high doses, and since the efficacy of the middle and high doses is lower than previous scenarios, we see more trials here that drop the low dose and continue the trial with only the placebo, middle dose, and high dose. There were 4620 trials that dropped the low dose at the first interim. Of those, 2319 trials met early success at the next interim (thus ending the trial), while 122 of the trials stopped for futility at the next interim and 2179 continued to the final analysis. Thus, for these 2179 trials, the final sample size for the low dose was 9 subjects, while the middle and high doses each had a final sample size of 17 subjects (each arm receiving two extra subjects because of the low dose dropping at the first interim). Additionally, there were 323 trials that continued all arms at the first interim, then dropped the low dose at the second interim. In these trials, the final sample size for the low dose was 12 subjects while the middle and high doses each received one extra subject for a total of 16 subjects at the final analysis.

Pr(Success)	Pr(Early Win)	Pr(Early Futility)
0.910	0.653	0.047

Mean Sample Size

Placebo	Low	Mid	High	Total
12.1	9.6	12.2	12.2	46.2

None	Low	Mid	High
0.090	0.001	0.451	0.458

[figure not shown]
Figure 10 Operating Characteristics for Scenario 4: 0.01, 0.10, 0.40, 0.50

Date: 07 Dec 2017 E-Statistical Analysis Plan-21977; Ver. 1.0 Supersedes: None Page 49 of 59

Scenario 5: 0.01, 0.10, 0.40, 0.40

In this scenario, the middle and high doses are equivalent with a 40% response rate. The low dose is 30% lower than the middle and high doses.

Roughly half of the simulated trials (5185 trials, or 51.9%) dropped the low dose at the first interim, but continued enrolling the other arms. An additional 482 trials (4.8%) dropped the low dose at the second interim. With the high probability of dropping the low dose, the average sample size for the low dose is 9.9 while the middle and high doses tend to have larger sample sizes, since they receive re-allocated subjects from the dropped low dose. The power for this scenario is 80.7%. The probability of early futility is 10.6% (5.5% at the first interim and 5.1% at the second interim).

Pr(Success)	Pr(Early Win)	Pr(Early Futility)
0.807	0.471	0.106

Mean Sample Size

mean cample offe					

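### The futility stop sets a hard 0.05 limit against an estimate from only 1000 random draws, so at some reachable interim results the seed decides whether the trial ends

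*SAP*

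**What the plan says.** The futility criterion in SAP 9.2.1.1 looks ahead to whether "the primary analysis will meet the success threshold once all arms have n = 15 subjects". For each arm the number of future responders follows a Beta-Binomial distribution, and a prior with "parameters a = 0.5 and b = 0.5 is used independently for each arm". The calculation is by sampling: "A large number of predicted values are sampled from the Beta-Binomial distribution for each arm, resulting in 1000" completed data sets. "The predictive probability of eventual trial success is then the proportion of these complete datasets" that reach p < 0.0131. The consequence is firm: "If the predictive probability is less than 0.05, then the trial will be declared as a failure" and stops.

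The SAP gives no seed, no allowance for Monte Carlo error and no rule for values close to 0.05. SAP 15.2.5 says only that the simulations used custom R code. Table 3, which supports the low-dose threshold and decides nothing during the trial, used 10,000 predictions, ten times as many as the futility decision.

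**The concern.** The sampled proportion is itself the decision statistic. If its Monte Carlo error is comparable with the distance between the true predictive probability and 0.05, the same data under the same rule can stop the trial on one run and continue it on the next. A futility stop cannot be undone, and an auditor repeating the calculation could obtain the opposite answer. Sampling is also unnecessary, because with so few subjects outstanding the probability can be summed exactly.

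**Working it through.** **Inputs.** From SAP 9.2.1.1: Beta(0.5, 0.5) priors, final n = 15 per arm, success at p < 0.0131, 1000 draws, stop if the estimate is below 0.05. From SAP 9: looks at about 9 and 12 per arm. From SAP 15.2.3: the scenario response rates. The test is the one-sided Fisher test of the pooled 15 and 20 µg arms against placebo, unstratified, because this reproduces the SAP's example p-values (0.0052, 0.0197, 0.0139).

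**Formulas.** With n subjects and x responders in an arm and m = 15 − n still to come:

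- Exact PP = sum, over all future counts in placebo, middle and high, of the product of BetaBinomial(z; m, 0.5 + x, 0.5 + n − x), counting only outcomes with Fisher p < 0.0131. There are 7 × 7 × 7 = 343 outcomes at look 1 and 4 × 4 × 4 = 64 at look 2.
- Chance that a 1000-draw run stops = P(Binomial(1000, PP) ≤ 49).
- Monte Carlo standard error at the limit = √(0.05 × 0.95 / 1000) = 0.0069, a 95% band of about 0.036 to 0.064.

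**Reproducing the SAP's figures.** Example Trial 5 (0/9, 1/9, 2/9): exact 0.0121, printed 0.015, which is 0.8 standard errors apart. Example Trial 3 (0/9, 3/9, 5/9): exact 87.5%; the SAP says "The predictive probability of eventual trial success is 86.1" per cent, 1.4 standard errors apart. Both fit a 1000-draw estimate. Neither is near 0.05, so neither decision is in doubt.

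Futility rates (look 1 + look 2), by full enumeration of both looks:

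| Scenario | Exact PP | 1000-draw rule | Printed |
|---|---|---|---|
| 4 | 2.6% + 2.0% | 2.5% + 2.4% | 2.4% + 2.3% |
| 5 | 5.6% + 4.2% | 5.5% + 5.2% | 5.5% + 5.1% |
| 6 | 36.4% in total | 37.9% in total | 37.5% in total |

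For Scenario 5 the SAP states: "The probability of early futility is 10.6% (5.5% at the first interim and 5.1% at the second interim"). With 10,000 simulated trials the error on 4.2% is √(0.042 × 0.958 / 10,000) = 0.2 points. The printed 5.1% is therefore more than 4 standard errors from the exact rule, and it agrees with the 1000-draw rule.

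**Results near the limit.** Responders are listed as placebo, then the two higher doses in either order.

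| Look | Responders | Exact PP | Exact decision | Chance a 1000-draw run stops |
|---|---|---|---|---|
| 1 (9 per arm) | 0, 0, 4 | 0.0492 | stop | 52% |
| 1 | 1, 1, 5 | 0.0466 | stop | 67% |
| 1 | 1, 2, 4 | 0.0578 | continue | 13% |
| 2 (12 per arm) | 0, 1, 5 | 0.0409 | stop | 91% |
| 2 | 0, 2, 4 | 0.0527 | continue | 33% |
| 2 | 0, 3, 3 | 0.0563 | continue | 18% |

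With a placebo rate of 1%, zero placebo responders is the expected result, so the rows starting with 0 are reachable.

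**How often it matters.** The share of trials that meet a result with a stop chance between 5% and 95% is 15.9% in Scenario 6, 6.1% in Scenario 5, 3.1% in Scenario 4, 0.2% in Scenario 3, at most 0.04% in Scenarios 1 and 2, and about 0 in Scenario 7. At a result with stop chance s, two independent runs disagree with probability 2s(1 − s). Weighted by how often each result occurs, this gives 0.58% + 1.47% ≈ 2.1% of trials in Scenario 5 and 2.08% + 3.60% ≈ 5.7% in Scenario 6.

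**Sensitivity.** If the look-2 projection used n = 17 after a low-dose drop, the borderline results would move (0, 0, 5 stops in 66% of runs; 1, 1, 7 in 55%) but would not disappear. The shares would become 11.1% in Scenario 6 and 4.2% in Scenario 5.

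**The case against.** The strongest reply is about size.

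- **Power.** Exact against 1000-draw futility gives 90.95% against 90.84% in Scenario 4, 80.6% against 80.3% in Scenario 5, and 42.6% against 42.4% in Scenario 6 (n = 17 at the final analysis after a look-1 drop; the n = 16 case ignored). Type I error is untouched. This stands.
- **Scenarios.** The planning rates of 70/65/60/1% are Scenario 1, where borderline results hardly occur. The near coin-flip result 0, 0, 4 arises in 0.46% of Scenario 5 trials and 3.1% of Scenario 6 trials. This stands too. The two-seed disagreement rates of 2.1% and 5.7% are the fairer measure, since the 6% and 16% include results where 91% of runs agree.
- **Stakes.** Where the seed matters most, the true predictive probability is close to 0.05, so stopping and continuing are nearly equivalent by the plan's own measure. That is fair as to expected loss, but it does not make the decision reproducible.
- **Printed rates.** They describe the rule as written correctly and need restating only if the rule changes. Agreed.
- **Discretion.** Protocol 9.6.1 and the opening of SAP 9 say only that the trial may terminate, a data monitoring committee advises, and the interim process sits in a separate document that could fix a seed. SAP 9.2.1.1 is nevertheless firm, and neither document gives a criterion for borderline values. A fixed seed would make the run repeatable, but the answer would still depend on which seed was chosen.
- **Stratification.** The primary test is stratified by randomization scheme, so an exact sum must place future subjects in strata. True, but the SAP's own sampling needs the same allocation.

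**Conclusion.** The concern holds. The rule compares a noisy estimate with a strict limit, and at several reachable results the seed has a material say in whether the trial ends. The effect is confined to weak or moderate treatment effects, with pooled rates of about 20% to 40%. It is negligible under the planning rates and the null, and it costs at most about 0.3 points of power. It should be corrected because the decision is irreversible and an exact answer is available at almost no cost; it is not a threat to the validity of the primary test.

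The figures assume the unstratified Fisher test, exactly 9 and 12 evaluable subjects per arm, and a low-dose drop on strict inequality (1). Stratification or unequal arms would change which results are borderline.

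**What to change.** In SAP 9.2.1.1, replace the 1000 sampled data sets by the exact sum of Beta-Binomial probabilities over all remaining outcomes, with the same stratified test as the primary analysis, and state how outstanding subjects are assigned to randomization schemes. Then restate the futility rates in SAP 15.2.3 and the predictive probabilities in the SAP 15.2.2 examples on that basis.

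If simulation is kept as a check, use at least 1,000,000 draws with a seed fixed in advance. The standard error is then √(0.05 × 0.95 / 1,000,000) = 0.0002, against a smallest gap in the table of 0.0500 − 0.0492 = 0.0008. The 10,000 draws used for Table 3 would not be enough: 0, 0, 4 at look 1 would still stop in only 63% of runs, and 0, 2, 4 at look 2 would stop in 11%.

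The cost is a few lines of code, one SAP sentence and a rerun of the simulations. Nothing that subjects or sites do changes.
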